6.5. Baseline and Other Summaries and Analyses

6.5.1. Baseline Summaries

Demographics, medical history, primary diagnosis, history of prior AD treatments and disease characteristics including variables defined in [Section 3.5](#) and SCORAD (VAS) of Sleep Loss will be summarized by treatment group according to CaPS. Baseline disease severity based on IGA and baseline EASI score will also be summarized by gender.

6.5.2. Study Conduct and Participant Disposition

Participants evaluation, disposition, discontinuation will be summarized according to CaPS.

¹ For purposes of analysis, Other will comprise the categories of American Indian or Alaska Native, Native Hawaiian or Other Pacific Islander, Multi-Racial and any other category reported on the CRF.

6.5.3. Study Treatment Exposure

6.5.3.1. Oral Dosing

- Duration of Treatment is defined as the total number of dosing days on which study oral drug was actually administered; if N doses missed on unknown dates, it reduces the Duration of Treatment by N/2 (when N is an event number) or (N-1)/2 (when N is an odd number);
- Exposure Time is defined as the total number of days from first to and including last day of study oral dosing (Last Oral Dosing Date - First Oral Dosing Date + 1);
- Dose Compliance is defined as the number of doses of study drug the participant took out of the expected total number of doses of study drug.
 - Expected Number of Doses = 2*(Exposure Time);
 - Dose Compliance = (Total Actual Oral Pills/Expected Number of Doses) * 100%.

Study intervention may be temporarily withheld for a maximum of 28 days at investigator's discretion due to abnormal laboratory tests or adverse event (Protocol Section 6.4). The Dose Compliance does not consider whether missed doses were due to protocol-allowed temporary withholding.

Number, mean, standard deviation, median, minimum and maximum will be presented for those variables: Duration of Treatment, Exposure Time and Dose Compliance. Number and percent will be reported for participants in Duration of Treatment categories (<1 Week, >=1 Week to 4 Weeks, >=4 Weeks to 8 Weeks, >=8 Weeks to 12 Weeks, ..., >=20 Weeks to 24 Weeks, >= 24 Weeks), and Dose Compliance <80% and Dose Compliance >120%.

6.5.3.2. Injection Dosing

Dupilumab or its matching placebo is administered every other week from Day 1 to Week 24, with two loading doses at baseline and then one dose each time, and last injection will occur at Week 24.

- Exposure Time of Injection = (Last Injection Date - First Injection Date + 14); eg, for subject receiving only the loading doses at baseline, the Exposure Time of Injection should be 14 days;
- Expected Number of Injections during the exposure period will be based on [Appendix 4](#);
- Injection Dose Compliance = (Total Actual Injections/Expected Number of Injections) * 100%

Number, mean, standard deviation, median, minimum and maximum will be presented for those variables: Exposure Time of Injection, Number of Injections Received, Injection Dose

Compliance. Number and percent will be reported for with Injection Dose Compliance <80% and Injection Dose Compliance >120%.

6.5.4. Concomitant/Background Medications and Non-Drug Treatments

Prior drug and non-drug treatment, concomitant drug and non-drug treatment will be summarized according to CaPS.

6.5.4.1. Background Topical Therapy (Medicated and Non-Medicated)

Number and percent of participants used non-medicated emollient, medicated topical therapy, topical corticosteroids (TCS), topical calcineurin inhibitors (TCI), topical PDE4 inhibitors will be reported during the study treatment dosing period.

6.5.4.2. Rescue Therapy for AD

Number and percent will be presented for participants who used rescue therapy, then summarized by topical and systemic groups.

6.5.5. Per-Protocol Analysis Set

The listing of subjects excluded from PPAS and reasons for exclusion will be provided. The number and percent of subjects excluded from PPAS, the number and percent of each reasons why subjects were excluded from PPAS will also be presented for each treatment arm.

For the purpose of PPAS, Week 16 is defined as the date of visit used for Week 16 EASI analysis. If a participant's Week 16 EASI is missing, Week 16 is defined as Day 113 relative to Day 1. Oral dose compliance ([Section 6.5.3.1](#)) and Injection dose compliance ([Section 6.5.3.2](#)) will also be summarized at Week 16.

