7.1.1. Temporary Discontinuation

An investigator can temporarily interrupt oral study intervention for up to a maximum of 28 consecutive days and up to 2 consecutive doses of injectable study intervention for a participant, for safety reasons or while monitoring abnormal laboratory tests if the investigator judges that this is necessary. In the case of study intervention(s) being withheld, all study intervention(s) that the participant is receiving should be withheld (ie, both oral and injected study intervention, as applicable). The investigator should use their judgement with regard to unscheduled visits/laboratory/clinical assessments required to monitor the participant during this timeframe. If within this timeframe the investigator judges that it is

safe to restart dosing, then the participant may restart the study intervention. If the investigator judges that it is not safe to restart dosing within this timeframe then the participant must be permanently discontinued from study intervention, have an End of Treatment visit, and enter the 4-week follow-up period (See Section 10.12.3 for UK country-specific requirements). Doses not taken for the reasons mentioned above do not constitute protocol deviations or medication errors and should not be considered dosing errors but should be noted in the dosing log with the reason for reduced drug consumption clearly described.

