4. ANALYSIS SETS (POPULATIONS FOR ANALYSIS)

Data for all participants will be assessed to determine if participants meet the criteria for inclusion in each analysis population prior to unblinding and releasing the database and classifications will be documented per standard operating procedures.

For purposes of analysis, the following populations are defined:

Population	Description
Enrolled	All participants who sign the ICD.
Randomly Assigned to Study Intervention	All participants who were randomly assigned to abrocitinib or dupilumab.
Full Analysis Set (FAS)	All randomized participants receiving at least one dose of study intervention. Participants will be analyzed according to the intervention to which they were randomized.
Per-Protocol Analysis Set (PPAS)	All randomized participants receiving at least one dose of study intervention who had no major protocol violations. This set will include participants who:

Population	Description
	
 • Were eligible for the study by way of meeting key inclusion criteria and none of the key exclusion criteria. • met I/E criteria of qualifying age • meet I/E criteria of baseline EASI ≥ 16 • meet I/E criteria of prior qualifying treatment • Had actual, observed EASI scores at Week 16. • Took the correct randomized treatment for at least 80% and at most 120% of the assigned amount until Week 16. • Had no other major protocol violations as determined by the clinical team prior to database lock. A major protocol violation in this context is one that is likely to affect materially the efficacy responses of the patient and will be defined by the clinical team before database is locked and any analysis is performed for this study.
Safety	All participants randomly assigned to study intervention and who take at least 1 dose of study intervention. Participants will be analyzed according to the intervention they actually received.

Unless otherwise specified, all observations after dropout or use of rescue therapy will be censored. In general, for the responder analysis, data after dropout or use of rescue therapy will be defined as “non-responsive” after that point.

[figure not shown]

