Appendix 2. Definition and Use of Visit Windows in Reporting

Unless otherwise specified, visit windows will be used for efficacy variables, and for any safety data that display or summarize by study visit. For other endpoints (eg, ECG, vital signs), visit windows will be applied for summary statistics by study visits if required.

Visit Label	Target Day	Definition [Day window]
Screening		Days -28 to Day -1
Baseline	Day 1 (Day of first dose), Baseline	Day 1
Week 2	15	Days 2 to 22
Week 4	29	Days 23 to 43
Week 8	57	Days 44 to 71
Week 12	85	Days 72 to 99
Week 16	113	Days 100 to 127
Week 20	141	Days 128 to 155
Week 24	169	Days 156 to 176
Week 26	183	Days 177 to 197
Follow Up/End of Study		
Week 30	-	Days 198 to -

If there are both observed records and missing records within the same visits window, the observed record will be used.

For the lab values, if the calculated study day for the labelled baseline visit is not study Day 1 but falls within 28 days before the start of the study dosing, then that data should be used for the baseline instead of leaving baseline missing.

For the other values, if the calculated study day for the labelled baseline visit is not study Day 1, but falls before the start of the study dosing, then that data should be used for the baseline instead of leaving baseline missing.

If two or more visits fall into the same window, keep the one closest to the Target Day. If two visits are equaled distant from the Target Day in absolute value, the later visit should be used.

If two or more values are collected on the same day: for measurements with labeled visits, the value where collect visit = analysis visit will be used; for measurements without labeled

visits but with time of collection, the last measurement of the day will be used for the analysis.

PP-NRS is recorded every day throughout the study. Observations on the actual day will be used to analyze Days 2-15 PP-NRS, and to derive the time to achieve PP-NRS4 response. Weeks 2, 4, 8, 12, 16, 20 and 26 PP-NRS response will be based on the windowing method.

Safety analysis may follow Pfizer standards.

For Estimand 1 and 2, data after rescue therapy will be censored first. The remaining observation will be mapped to the analysis visits.

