Appendix 4. Expected Number of Injections

Expected Number of Injections (Cumulative) will be based on Last Injection Date relative to Day 1/Baseline, using the following table:

Injection Schedule	Target Day	Window	Expected Number of Injections (Cumulative)
Baseline	Day 1	Days 1 to 7	2
Week 2	Day 15	Days 8 to 21	3
Week 4	Day 29	Days 22 to 35	4
Week 6	Day 43	Days 36 to 49	5
Week 8	Day 57	Days 50 to 63	6
Week 10	Day 71	Days 64 to 77	7
Week 12	Day 85	Days 78 to 91	8
Week 14	Day 99	Days 92 to 105	9
Week 16	Day 113	Days 106 to 119	10
Week 18	Day 127	Days 120 to 133	11
Week 20	Day 141	Days 134 to 147	12
Week 22	Day 155	Days 148 to 161	13
Week 24	Day 169	Days 162 to -	14

Eg, if a subject receives his/her last injection on Day 76, the Expected Number of Injections (Cumulative) should be 7.

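### The compliance formulas cited for the per-protocol set stop at the last dose, so an unresumed oral interruption running up to Week 16 can score 100% when under 80% was taken

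*SAP*

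**What the plan says.** The PPAS definition in SAP Section 4 requires an observed Week 16 EASI and that the participant "Took the correct randomized treatment for at least 80% and at most 120% of the assigned amount until Week 16".

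SAP 6.5.5 adds: "For the purpose of PPAS, Week 16 is defined as the date of visit used for Week 16 EASI analysis", with Day 113 as the fallback when that EASI is missing. It then says that oral and injection compliance, as defined in 6.5.3.1 and 6.5.3.2, will be summarised at Week 16 too. It does not change either definition.

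- **Oral (6.5.3.1).** "Exposure Time is defined as the total number of days from first to and including last day of study oral dosing". The expected number of tablets is twice that exposure time. The same section says compliance makes no allowance for doses missed through permitted withholding.
- **Injections (6.5.3.2 and Appendix 4).** "Expected Number of Injections (Cumulative) will be based on Last Injection Date relative to Day 1/Baseline".

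Appendix 2 accepts a Week 16 EASI from "Days 100 to 127". Protocol 7.1.1 lets the investigator "temporarily interrupt oral study intervention for up to a maximum of 28 consecutive days", and withhold up to two consecutive injections. It adds: "Doses not taken for the reasons mentioned above do not constitute protocol deviations or medication errors".

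**The concern.** The membership rule runs to Week 16, but the only written compliance formulas run to the last dose. A gap in the middle of dosing lowers the score. The same gap at the end vanishes from the denominator. This sits badly with the statement in 6.5.3.1 that withheld doses are not excused.

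A participant who took under 80% of the assigned amount could therefore meet the PPAS compliance criterion. The separate criterion on other major violations need not catch this, because the protocol says permitted withholding is not a deviation. Week 16 EASI-90 carries the non-inferiority test, and this is its only per-protocol analysis, so its membership should be reproducible and should match Section 4.

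**Working it through.** **The plan's own examples.** Appendix 4 says a last injection on Day 76 gives 7 expected injections. Day 76 lies in the row for Days 64 to 77, which gives 7. In 6.5.3.2, loading doses only give 1 - 1 + 14 = 14 days of exposure. Both reproduce, and both confirm that the last dose sets the end point.

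**Oral formulas.** Day 1 is the first dosing day, two tablets are due daily, and dosing is otherwise perfect. Let L be the last dosing day and D the Week 16 day.

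- As written: 2L / (2 x L) = 100% for every L.
- Against the amount assigned to Week 16: 2L / (2 x D) = L/D.

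**Example.** Interruption on Days 86 to 113, not resumed, EASI observed on Day 113: L = 85, D = 113.

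- As written: 170/170 = 100%.
- To Week 16: 170/226 = 75.2%. Leaving out the end-of-visit Day 113 dose gives 170/224 = 75.9%.

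**Which interruptions are misclassified.** Days 100 and 127 are the limits of the Appendix 2 window. Days 110 and 116 are the limits of the scheduled visit (Day 113 ±3).

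| Week 16 day | Shortest gap under 80% | One day shorter | 28-day gap |
|---|---|---|---|
| 100 | 21 days: 79/100 = 79.0% | 80/100 = 80.0% | 72/100 = 72.0% |
| 110 | 23 days: 87/110 = 79.1% | 88/110 = 80.0% | 82/110 = 74.5% |
| 113 | 23 days: 90/113 = 79.6% | 91/113 = 80.5% | 85/113 = 75.2% |
| 116 | 24 days: 92/116 = 79.3% | 93/116 = 80.2% | 88/116 = 75.9% |
| 127 | 26 days: 101/127 = 79.5% | 102/127 = 80.3% | 99/127 = 78.0% |

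The visit-day dose matters at the boundary: a last dose on Day 90 gives 90/113 = 79.6% with the Day 113 dose counted as due, and 90/112 = 80.4% without it.

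**If dosing resumes after Day 85.**

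- On Day 113: 172/226 = 76.1%, so the written formula catches the gap.
- On Day 114, exposure truncated at Week 16: 170/226 = 75.2%.
- On Day 114, later dosing records simply dropped: 170/170 = 100%.
- On Day 114, run to Day 183: 2 x (183 - 28) / (2 x 183) = 310/366 = 84.7%.

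Only truncating exposure matches Section 4 for the Day 114 case. The SAP does not say which is meant.

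**Injections, Week 16 on Day 113.** A last injection on Day 85 means 8 received, and missing Days 99 and 113 is the permitted maximum. As written: 8/8 = 100%. Against the Week 16 row: 8/10 = 80%, or 8/9 = 88.9% without the visit-day injection. It passes on every basis. If the Week 16 EASI falls on Days 120 to 127, the Appendix 4 row is 11 and already includes the injection due on Day 127: 8/11 = 72.7% with it, 8/10 = 80% without. A last injection on Day 71 gives 7/10 = 70% at Day 113, but three missed injections exceed the permitted interruption and may be excluded as a deviation.

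**Can such a participant have a Week 16 EASI?** Yes. A participant on hold can attend the Day 113 visit and then not restart. Alternatively, under protocol 7.3 the end-of-treatment visit falls within a week of the last dose, so a Day 85 last dose puts the follow-up visit four weeks later at about Days 113 to 120. EASI is scheduled there, and those days map to Week 16.

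**The case against.** The strongest reply is that Section 4 already sets the denominator: the amount assigned until Week 16, with no mention of the last dose. On this reading, 6.5.5 cites the formulas only for an added descriptive summary. The Day 113 fallback also suggests that compliance was meant to run to the Week 16 date, since participants without that EASI fail the PPAS anyway. This reading is possible, and a careful programmer might adopt it. But no formula implementing it is written, and the Week 16 summary does cite the last-dose formulas, so that table would be wrong whichever rule decides membership.

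The case is also narrow: a permitted hold of roughly three to four weeks that ends at Week 16 without resumption. Unexcused oral gaps of more than four days are medication errors discussed for possible withdrawal. Both points stand, and they limit the number of participants affected.

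Finally, a participant who is not restarted is permanently discontinued. If that counts as dropping out, the PPAS analysis scores a non-response, so the error need not add a false responder. This stands too, although the SAP does not define drop-out precisely. Membership would still not match Section 4.

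The clinical team's review before unblinding is a partial safeguard, weakened by protocol 7.1.1 for the permitted holds at issue.

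**Conclusion.** The concern holds, as a minor one. As written, the cited oral formula gives 100% to a participant who took 75.2% of the tablets assigned to Day 113. With Week 16 on Day 113, it misclassifies unresumed interruptions of 23 to 28 days. A full 28-day unresumed interruption is under 80% at every date in the Week 16 window (72.0% to 78.0%).

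This assumes otherwise perfect dosing. For PPAS membership it also rests on the inference that the 6.5.3 formulas are the ones applied; for the Week 16 compliance summary no inference is needed. Permitted injection interruptions do not produce the error when Week 16 is on Day 113.

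The effect is confined to Supplementary Analysis 1 of Week 16 EASI-90 and the Week 16 compliance summary. The non-inferiority and superiority tests on the full analysis set are unaffected. The number of participants involved is probably small and cannot be derived from the documents.

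**What to change.** In SAP 6.5.5, for both PPAS membership and the Week 16 compliance summary, state that:

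- expected oral tablets = 2 x (Week 16 date - Day 1 date + 1);
- expected injections = the Appendix 4 row containing the Week 16 date defined in 6.5.5;
- only doses taken up to that date are counted;
- a dose due at the Week 16 visit is treated the same way in numerator and denominator, and the text says whether an injection whose target day falls after the Week 16 date counts as expected;
- these rules decide PPAS membership.

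Keep the last-dose definitions of 6.5.3 and Appendix 4 for the overall exposure tables.

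The cost is a few sentences and a small programming change, made before unblinding, with no protocol amendment. The PPAS may become slightly smaller.

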6.6. Safety Summaries and Analyses

Safety analysis will be based on the SAF analysis set.

All clinical AEs, SAEs, treatment-emergent signs and symptoms (TEAEs), withdrawal due to AEs, ECGs, vital signs and safety laboratory data will be reviewed and summarized on an ongoing basis during the study to evaluate the safety of participants.

Safety data will be presented in tabular and/or graphical format and summarized descriptively, where appropriate. All safety endpoints will be listed and summarized in accordance with CaPS. Categorical outcomes (eg, AEs) will be summarized by participant counts and percentage. Continuous outcome (eg, blood pressure, pulse rate, etc.) will be summarized using N, mean, median, standard deviation, etc. Change from baseline in laboratory data, ECGs, physical exams and vital signs will also be summarized. Participant listings will be produced for these safety endpoints accordingly.

6.6.1. Adverse Events

The safety data will be summarized in accordance with CaPS. All safety data will be summarized descriptively through appropriate data tabulations, descriptive statistics, categorical summaries, and graphical presentations. Safety endpoints for the study include:

- Treatment-emergent AEs and SAEs;
- Withdrawals from active treatment due to AEs;

Adverse events of special interest are the following:

- Serious infections, defined as serious adverse events in System Organ Class Infections And Infestations;
- Herpes zoster defined by Customized MedDRA Queries.
- Conjunctivitis defined by Conjunctivitis details CRF page
- Acne and folliculitis defined by Acne and Folliculitis details CRF page

The incidence and severity of AE of special interest will be reported by System Organ Class and Preferred Term.

It should be recognized that most studies are not designed to reliably demonstrate a causal relationship between the use of a pharmaceutical product and an adverse event or a group of adverse events. Except for selected events in unique situations, studies do not employ formal adjudication procedures for event classification. As such, safety analysis is generally considered as an exploratory analysis and its purpose is to generate hypotheses for further investigation.

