Appendix 8.2.6. Adverse Event of Special Interest53

1. VERSION HISTORY

Table 1. Summary of Changes

Version/ Date	Associated Protocol Amendment	Rationale	Specific Changes
1 17 Jan 2020	Original 04 Nov 2019	N/A	N/A
2 21 Jul 2021	Amendment 2 14 Aug 2019	Modifications and clarifications of planned analyses to align with across the program. Deleted endpoints not used for CSR purpose, and added endpoints of interest.	
 • EASI-75 in the primary, key secondary and secondary endpoints was changed to EASI-90. EASI-90 in one of the secondary endpoints was changed to EASI-75. • Added responder analysis based on DLQI in Section 2, Section 3.3 and Section 6.2. • Deleted exploratory endpoints in Section 2 • Updated the name of estimand 3 in section 2, section 5 and section 6. • Updated the definition of baseline variables in section 3.5. • Deleted 3-tier approach for summarizing AE in Section 3.6.1, Section 5.2.6 and Section 6.6.1. • Updated the definition of PPAS in section 4. • Updated the hypotheses and decision rules to reflect the changes in primary end key secondary endpoints; and to include testing for PP-NRS4 from Week 2 to earlier time points in section 5.1. • Updated the definition of medicated topical background therapy free days in Section 6.2.2.4.

Table 1. Summary of Changes

Version/ Date	Associated Protocol Amendment	Rationale	Specific Changes
			
 • Updated subsets analyses in Section 6.4. • Updated rescue therapy summaries in Section 6.5.4.2. • Updated adverse event of special interest in Section 6.6.1. • Deleted Acne and Folliculitis details in section 6.6.7. • Updated the definition of visit window in Appendix 2. • Included additional analyses (not for CSR purpose) in Appendix 8. • Additional minor changes to improve clarity and alignment with the protocol.

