	
clear (0) or almost clear (1) (on a 5-point scale) and a reduction from baseline of ≥ 2 points at all scheduled time points up to Week 26;
 
 • Response based on achieving at least a 4-point improvement in the severity of PP-NRS from baseline at all scheduled time points except Week 2; • Time from baseline to achieve at least a 4-point improvement in the severity of PP-NRS scale; • Percent Change from Baseline in the % Body Surface Area (BSA) affected at all scheduled time points; • Percent Change from Baseline in the SCORing Atopic Dermatitis (SCORAD) at all scheduled timepoints; • Change from baseline in the Hospital Anxiety and Depression Scale (HADS) at all scheduled timepoints; • Change from baseline in Dermatology Life Quality Index (DLQI) at all scheduled time points; • Change from baseline in EuroQol Quality of Life 5-Dimension 5-Level Scale (EQ-5D-5L) at all scheduled time points; • Change from baseline in Patient-Oriented Eczema Measure (POEM) at all scheduled time points; • Change from baseline in Medical Outcomes Study – Sleep Scale (MOS-

Table 2. Study Objectives and Endpoints

Objectives	Endpoints
	
Sleep Scale) at all scheduled time points;
 
 • Change from baseline in Skin Pain NRS at all scheduled time points; • Medicated topical background therapy-free days. • DLQI ≥ 4 Points Improvement from Baseline Response at all scheduled time points;
Safety	

 • To compare the safety and tolerability of abrocitinib 200 mg QD versus dupilumab in adult participants on background topical therapy with moderate to severe AD. 	
 • Incidence of treatment-emergent adverse event (AE)s; • Incidence of serious adverse event (SAE)s and AEs leading to discontinuation; • Incidence of clinical abnormalities and change from baseline in clinical laboratory values, electrocardiogram (ECG) measurements, and vital signs.

There are 2 main estimands (Estimand 1 and Estimand 2) for the study. Estimand 3 and Estimand 4 will be used for supplemental analyses of the primary and key secondary endpoints.

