5.2. General Methods

In general, for descriptive analyses, number and percent will be presented for binary variables. Number, mean, standard deviation, median, first and third quartiles will be presented for continuous variables. For efficacy measures, descriptive analyses will be provided for PP-NRS and EASI.

Estimates of treatment difference between abrocitinib and dupilumab along with its two-sided 95% confidence interval and p-value will be provided. There will be no claims of statistical significance for treatment comparisons unless an exception is noted in Section 5.1 or Section 6 or any of its subsections.

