5.2.4. Analyses for Categorical Endpoints

The frequency and percentage for each category will be presented.

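### The safety objective is to compare abrocitinib with dupilumab, but SAP 6.6 specifies only descriptive summaries and names no between-arm estimate or interval.

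*SAP*

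**What the plan says.** The safety row of SAP Table 2 (Section 2.1) gives the objective as "To compare the safety and tolerability of abrocitinib 200 mg QD versus dupilumab in adult participants on background topical therapy". The objectives table in Protocol Section 3 sets the same comparative aim. The endpoints listed beside it are incidences of treatment-emergent AEs, of SAEs and AEs leading to discontinuation, and of clinical abnormalities, with changes from baseline in laboratory values, ECG and vital signs.

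The planned analysis is descriptive throughout:

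- SAP 6.6: "Categorical outcomes (eg, AEs) will be summarized by participant counts and percentage".
- SAP 6.6.1: "All safety data will be summarized descriptively through appropriate data tabulations, descriptive statistics, categorical summaries, and graphical presentations".
- SAP 5.2.4, the method for categorical data: "The frequency and percentage for each category will be presented".
- SAP 6.6.1 also sets the status of the work: "safety analysis is generally considered as an exploratory analysis and its purpose is to generate hypotheses for further investigation".

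The protocol plans the same kind of summary in its synopsis and in Section 9.4.3.

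One sentence in SAP 5.2 (General Methods) points the other way: "Estimates of treatment difference between abrocitinib and dupilumab along with its two-sided 95% confidence interval and p-value will be provided". It directly follows the paragraph on descriptive methods, which closes with efficacy measures. Section 6.6 does not refer to it.

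**The concern.** This is a head-to-head trial, and one of its stated aims is to compare safety. The documents give reason to look for differences in both directions. Protocol 2.2.2 reports more conjunctivitis with dupilumab than with placebo. Protocol 2.3 lists viral reactivation and serious infections among the potential risks of abrocitinib. Conjunctivitis, herpes zoster and serious infections are all events of special interest in SAP 6.6.1.

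If the tables show only a percentage for each drug, the reader sees that two percentages differ or agree but not how precisely the difference is estimated. For less common events, similar observed percentages can be compatible with a true difference of a few points either way. No estimate, type I error rate or trial decision is wrong because of this. What is missing is a stated precision for the comparison that the objective asks for.

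**Working it through.** **1. Is any between-arm safety estimate specified?**

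| Place | What it specifies for safety | Between-arm estimate or interval |
|---|---|---|
| SAP 2.1 and Protocol 3 | A comparative objective; incidence and change-from-baseline endpoints | Not addressed |
| SAP 5.2.4 | Frequency and percentage | None |
| SAP 6.6 | Counts and percentages; N, mean, median, SD; changes from baseline; listings | None |
| SAP 6.6.1 | Descriptive summaries; incidence and severity of special-interest events | None |
| SAP 6.6.2 | Participants meeting monitoring and discontinuation criteria, by the method of 5.2.4 | None |
| SAP Appendix 8.2.6 (not for the CSR) | Time of first event, probability of resolution, listings | None |
| Protocol synopsis and 9.4.3 | Descriptive summaries | None |
| SAP 5.2 | Difference, 95% CI and p-value, in general terms | Yes, but not tied to safety |

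**2. Can SAP 5.2 fill the gap?** If it governed safety, every safety comparison would carry a p-value. That does not fit 6.6, which names counts and percentages for AEs, or 6.6.1, which describes the analysis as descriptive and exploratory. The safety text is the more specific of the two and does not cite 5.2. The documents therefore do not settle the question in favour of intervals, and on either reading a clarifying line is needed.

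**3. What precision would an interval show?** The documents state no precision or power for safety, so there is no figure of theirs to reproduce. The only design input is 300 participants per arm (SAP 2.2, Protocol 9.2). With equal true incidence p in both arms, the Wald half-width is

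1.96 × √(2p(1 − p)/300).

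Assumed, illustrative incidences:

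- p = 0.02: 1.96 × √(0.0392/300) = 2.2 points
- p = 0.05: 1.96 × √(0.095/300) = 3.5 points
- p = 0.10: 1.96 × √(0.18/300) = 4.8 points
- p = 0.20: 1.96 × √(0.32/300) = 6.4 points

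Incidences for dupilumab every two weeks plus topical corticosteroid, from Protocol 2.2.2, applied to both arms:

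- any AE 72.0% (CAFÉ): 7.2 points; any AE 88% (CHRONOS): 5.2 points
- SAE 1.9% (CAFÉ): 2.2 points; SAE 4% (CHRONOS): 3.1 points

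**4. Does the interval method matter?** The Wald form is rough when events are few. Miettinen-Nurminen score intervals for assumed counts out of 300 per arm are:

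- 6 v 6 (2% in each arm): −2.5 to 2.5 points
- 12 v 12 (4% in each arm): −3.3 to 3.3 points
- 30 v 15 (10% v 5%): difference 5.0, interval 0.8 to 9.4 points

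At 2% and 4% the score interval is slightly wider than the Wald one (2.5 against 2.2, and 3.3 against 3.1), so a score interval is the better default. In the last example the bare percentages of 10% and 5% do not show that the difference could be anything from about 1 to about 9 points.

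**The case against.** The case on the other side is substantial.

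- **SAP 5.2 may already cover safety.** Its sentence stands as a separate paragraph and is not expressly limited to efficacy. This stands in part: a flat claim that the SAP provides no intervals anywhere would be wrong. What holds is that the safety sections do not invoke it and do not fit its p-values.
- **Safety outputs follow CaPS.** This sponsor reporting standard is not among the documents and may include between-arm estimates. That cannot be checked, and the SAP does not say so.
- **The scope is disclosed and consistent.** The SAP calls safety exploratory, and the protocol plans the same descriptive summary. This argues against hypothesis tests, and none is proposed here. It does not argue against estimation. SAP 6.4 already reports subgroup differences with a 95% interval, no p-value and no intended inference.
- **Incidence by arm is a comparison of a kind, and a reader can compute an interval from counts and denominators.** Both are true. The information is not lost; the plan does not undertake to present it.

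Two stronger readings are tempting. From the change log ("Deleted 3-tier approach for summarizing AE in Section 3.6.1, Section 5.2.6 and Section 6.6.1") and the Miettinen-Nurminen reference that remains in SAP Section 8 without being cited by any method, a reader might infer that a planned safety comparison was removed. The documents do not support this. The log describes superseded text, neither document says what the tiers contained, and nothing links the reference to safety. A reader might also infer that the trial yields only counts and leaves its safety objective unanswered. That goes too far, because the plan includes percentages, changes from baseline, severity of special-interest events and laboratory criteria.

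**Conclusion.** The point holds as a modest one. The objective is comparative, the safety sections name only descriptive summaries, and the one general sentence that could supply an interval is not tied to safety and would bring p-values with it. The objective is therefore answered by side-by-side percentages without stated precision.

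The precision left unstated runs from about ±2 points for events near 2% to about ±6 points for events near 20%. This rests on 300 treated participants per arm, equal true incidence in the two arms, and incidences chosen for illustration. The figures show how wide the intervals would be; they do not measure bias. No efficacy result, error rate or conduct decision depends on the point. It also rests on the SAP text as it stands, since the content of CaPS is unknown.

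**What to change.** In SAP 6.6.1, for any TEAE, SAEs, discontinuations due to AEs and each listed special-interest event (serious infections, herpes zoster, conjunctivitis, acne and folliculitis):

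- report the risk difference, abrocitinib minus dupilumab, with a 95% Miettinen-Nurminen interval;
- give no p-values;
- footnote the intervals as exploratory and unadjusted for multiplicity;
- state that the p-value sentence in SAP 5.2 does not apply to safety.

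If the sponsor does not want between-arm estimates, the alternative is to reword the safety objective as descriptive in both documents.

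The cost is a few extra columns in existing tables and two or three sentences in the SAP, with no change to design, data collection or the primary analysis. The downside is that unadjusted intervals across several event types may be over-read, with one that excludes zero taken as a finding. The footnote reduces that risk but does not remove it.
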